#### **13.1.2 Secondary Endpoints**

1. Number of patients experiencing lymphopenia, thrombocytopenia, neutropenia and anemia in each group as measured by standard blood draws. Thresholds for each event are listed in the table under Study Assessments below.
2. Score on FACT-BR quality of life survey between morning and evening treatment to quantitatively measure quality of life.
3. Progression-free survival as determined by chart review or patient visit.
4. Overall survival as determined by chart review or patient visit.
5. Correlation between sleep pattern and response to treatment in morning and evening groups.

## **13.2 Data Analysis**

### **13.2.1 General Considerations**

All data will be evaluated as observed, and no imputation method for missing values will be used. All data will be presented in a descriptive manner. Each cohort will be analyzed separately, and no multiplicity adjustment across cohorts will be

performed. All other analyses are considered as exploratory, even if statistical tests are used.

Descriptive statistics will be used to summarize the trial results, i.e., statistics for continuous variables may include means, medians, ranges and appropriate measures of variability. Qualitative variables will be summarized by counts and percentages. The uncertainty of estimates will be assessed by confidence intervals. Unless otherwise specified, the calculation of proportions will be based on the sample size of the population of interest. Counts of missing observations will be included in the denominator and presented as a separate category if not otherwise specified in the statistical analysis plan (SAP).

Duration of response, according to RANO, will be calculated for each subject and will be analyzed using the Kaplan-Meier method in the primary cohorts separately.

PFS will be presented in subject listings and analyzed using the Kaplan-Meier method in the primary cohorts separately.

Correlation analysis (significance at  $R^2 \geq 0.8$ ) and slope analysis (Fisher's Exact Test) of dependent variables (naps/day, nap duration, sleep duration, % activity during waking, % activity during sleep, chronotype, chronotype variability) and independent variables (tumor grade, time since TMZ administration, time of day of TMZ administration, time since diagnosis date, tumor size, immune health) will be carried out. Each variable will be calculated daily and averaged over the collection period. Daily calculation reveals stability, while the average reveals variability.

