## **7.0 CORRELATIVE STUDIES**

### **7.1 Quality of Life Surveys**

Patient quality of life will be assessed using a standard quality of life survey specifically designed for brain cancer patients (the FACT-Br, see Appendix C). QOL assessments will be performed at the following time points:

- baseline
- at the beginning of each cycle of chemotherapy
- 1 month after the final chemotherapy treatment.

The QOL surveys will be administered during an office visit by the study coordinator.

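### Section 13.2 gives no FACT-Br analysis: the general descriptive rule makes no provision for the baseline score and leaves later-cycle arm comparisons conditional on still being treated

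*Combined protocol and SAP*

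**What the plan says.** Section 13.1.2 lists the endpoint as "Score on FACT-BR quality of life survey between morning and evening treatment to quantitatively measure quality of life". It names no cycle, change score or subscale. Section 7.1 states that "QOL assessments will be performed at the following time points" and lists baseline, "at the beginning of each cycle of chemotherapy" and "1 month after the final chemotherapy treatment". The Study Calendar (9.0) and the Data Submission Schedule (10.0) agree.

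Section 13.2 has paragraphs on duration of response, PFS, the actimetry correlations, adverse events and laboratory data, but none on FACT-Br. The general text of 13.2.1 therefore governs: "All data will be evaluated as observed, and no imputation method for missing values will be used" and "All data will be presented in a descriptive manner". For continuous data, "statistics for continuous variables may include means, medians, ranges and appropriate measures of variability". Uncertainty is to be shown by confidence intervals, and "All other analyses are considered as exploratory, even if statistical tests are used". Output adjusted for baseline is mentioned only as an option for laboratory frequencies, in 13.2.2.2.

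**The concern.** The endpoint is a comparison between randomised arms, and the trial collects the covariate most likely to sharpen it, yet no analysis of the comparison is written down. A statistician following 13.2.1 would tabulate scores by arm and visit. Two things follow.

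First, nothing provides for the baseline score. In a trial of this size, between-patient spread in quality of life will dominate an unadjusted difference.

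Second, the cycle-start forms stop when a patient's cycles stop, whether through completion, toxicity, progression or death. A later-cycle arm mean is then a mean over patients still being treated. Section 1.7 hypothesises that dosing time alters efficacy and toxicity, so unequal retention between arms is a possibility that the trial's own hypothesis raises.

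Section 2.0 says that the study gathers pilot data for later chronotherapy trials. An imprecise quality-of-life estimate, or one whose population is unclear, would carry into their design.

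**Working it through.** **The plan's own figure.** There is none to reproduce for FACT-Br: no SD, effect size, power or precision target is stated. Section 13.0 gives 40 patients on a rule of thumb, and section 4.4 gives 1:1 allocation, so 40/2 = 20 per arm.

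**Inputs.** n = 20 per arm (sections 13.0 and 4.4). The correlation r between baseline and follow-up FACT-Br is not in the documents; I assume 0.5 to 0.7. Results are in units of the FACT-Br SD, which is also not given.

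**Formulas.** Standard error of the arm difference:
- unadjusted: √(2/n)
- baseline as covariate: √(2(1 − r²)/n)
- change from baseline: √(4(1 − r)/n)

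The 95% half-width is 1.96 × SE (normal approximation).

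**All 20 per arm observed.**
- Unadjusted: √(2/20) = 0.316; × 1.96 = 0.62 SD.
- Covariate, r = 0.5: √(2 × 0.75/20) = 0.274; half-width 0.54 SD.
- Covariate, r = 0.6: √(2 × 0.64/20) = 0.253; half-width 0.50 SD.
- Covariate, r = 0.7: √(2 × 0.51/20) = 0.226; half-width 0.44 SD.

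The equivalent gain in sample size is 1/(1 − r²): 1.33, 1.56 and 1.96.

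A plain change score does less well. Its SE is 0.316, 0.283 and 0.245, so its half-widths are 0.62, 0.55 and 0.48 SD. At r = 0.5 it gains nothing over ignoring baseline.

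**Fewer patients at later cycles.** The documents state neither a dropout rate nor a number of cycles. As a rough scale only, section 1.2 cites a median GBM survival of 14.6 months. With exponential survival (assumed), 0.5^(6/14.6) = 0.75 are alive at 6 months, or 15 of 20, and fewer would still be on treatment. The trial also admits grade II and III and recurrent tumours, so this is not a forecast.

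| Observed per arm | Unadjusted | r = 0.5 | r = 0.6 | r = 0.7 |
|---|---|---|---|---|
| 20 | 0.62 | 0.54 | 0.50 | 0.44 |
| 15 | 0.72 | 0.62 | 0.57 | 0.51 |
| 10 | 0.88 | 0.76 | 0.70 | 0.63 |

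**When the arm difference is biased.** Let d be the amount by which the mean among observed patients exceeds the mean among all patients in that arm who could have given a form. Then

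observed difference = difference among all + (d_morning − d_evening).

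If retention and selection are the same in both arms, the two d terms cancel: each arm mean may be too high, but the contrast is not distorted. If they differ, the contrast shifts by their difference, in either direction. Finding d requires dropout rates by arm, the dependence of dropout on score, and the SD. The documents give none of these, so no size is offered.

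**The case against.** The strongest reply has four parts.

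1. **Nothing says that baseline will be discarded.** A reader might infer from 13.2.1 that the plan rules out baseline adjustment. It does not. The rule is silent, its list of statistics is permissive, and a descriptive change from baseline would fit it. It does not even prescribe arm means by cycle.

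2. **The no-imputation sentence is not the cause.** A reader might take it as a rule that must be reversed. A likelihood-based repeated-measures model uses only observed forms and imputes nothing, so it complies. Section 13.2.1 also allows exploratory tests and calls for confidence intervals.

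3. **The on-treatment view fits the objective.** Secondary objective 2 in section 2.2 concerns patients while they receive temozolomide, so a summary restricted to treated patients answers a legitimate question. A mixed model implicitly extends scores past the end of treatment, and its estimates have no meaning after death. In addition, the form due 1 month after the last treatment also covers patients who stopped early, so not every post-baseline form is limited to those on treatment.

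4. **The stakes are limited.** This is one of five secondary endpoints in a descriptive feasibility study, with no decision attached.

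Parts 1 and 2 stand: the gap is an absent FACT-Br analysis, not a harmful rule. Part 3 stands as a reason to state the target population and the handling of death. It does not supply a use for baseline, and one post-treatment form at a patient-specific time does not fill missing cycles. Part 4 limits severity. It does not remove the point, because the better estimate uses scores already collected.

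**Conclusion.** The point holds as a missing analysis with a concrete, better alternative. The measurable cost is precision: by the calculation above, an analysis that ignores baseline gives an interval about 15% to 40% wider than necessary (0.62/0.54 = 1.15; 0.62/0.44 = 1.41). This rests on assumed correlations of 0.5 to 0.7 and a single follow-up visit. The normal approximation slightly understates all widths at this sample size.

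Later-cycle comparisons are conditional on remaining on treatment; that follows from the schedule itself. A reader might go further and infer that the arm difference is biased, or is pulled towards zero. The documents do not support that. It would need retention or selection to differ by arm, and the direction would depend on how they differ. Baseline adjustment alone would not cure such bias if patients leave because of a current decline that no form recorded.

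Severity is low to moderate: a secondary endpoint in a 40-patient feasibility study, with pilot estimates meant to inform later trials.

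**What to change.** Add a FACT-Br paragraph to section 13.2 and keep the descriptive table.

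- **Model.** A likelihood-based repeated-measures model on observed forms, without imputation: arm, cycle, arm-by-cycle, baseline FACT-Br and a patient random intercept. State which form is the baseline, since the form at the start of cycle 1 may also precede the first dose.
- **Report.** The adjusted morning-minus-evening difference with its 95% confidence interval at one pre-named early cycle after dosing has begun, and averaged over cycles. Label it exploratory.
- **Missing forms.** By arm and cycle, tabulate forms expected and received, with the reason for each missing form: treatment completed, stopped for another reason, progression, death, or form not completed.
- **Post-treatment form.** Summarise the 1-month form separately, because its timing differs between patients.
- **Limits to state.** The model assumes that forms are missing at random given the observed scores and covariates, and its estimates do not apply after death.

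The cost is SAP wording, one model and one table. No new assessments are needed, although the reason for each missing form must be recorded. The downside is reliance on the missing-at-random assumption, which the data cannot verify. The table of missing forms lets readers judge it.

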## **2.0 OBJECTIVES**

This exploratory study will collect pilot data for assessment of treatment outcomes in future glioma chronotherapeutic studies.

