### **2.2 Secondary Objectives**

1. To determine the number of HGG patients with grade 3 or 4 hematologic toxicity, including lymphopenia, thrombocytopenia, neutropenia and anemia, while receiving temozolomide when administered in the morning (before 10:00) or evening (after 20:00).
2. To assess quality of life using quality of life surveys in HGG patients receiving temozolomide in the morning versus evening.
3. To evaluate progression-free survival of HGG patients taking TMZ in the morning versus evening through chart review or patient visits.
4. To determine overall survival of HGG patients taking TMZ in the morning versus evening through chart review or patient visits.
5. To correlate the sleep-wake cycles of patients receiving temozolomide for treatment of HGG with treatment outcomes for morning versus evening TMZ treatments.

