## **7.2 Wrist Actimetry and Sleep Questionnaire**

The ActTrust Condor Instrument watches are wrist actimetry/accelerometers. Large datasets from these devices can be accessed and analyzed through ActStudio (Condor Instruments). This technology has been used already by several groups at Washington University in St. Louis.

Patients will wear an accelerometer on their wrist to measure activity level during the day and at night until two months after the end of treatment. The accelerometer will appear similar to an athletic wristwatch. Patients will be required to wear the accelerometer at all times starting at the beginning of treatment or as soon as they are enrolled in the study, whichever is later. Patients will remove the accelerometer only during situations when the accelerometer would be completely submersed in water or liquid. Wrist actigraphy will be quantified in one-minute bins for the duration of the recording (typically 60 days per patient). The data (counts per minute) will be quantified in terms of average activity per day, percent of activity during waking, percent of activity during sleep, chronotype (average time of daily mid-sleep), chronotype variability (e.g. cycle-to-cycle standard deviation of daily chronotype), sleep duration, nap duration, and number of naps per day. This data will be collected once every 2 months. Patients will not need to charge the watch and upon data collection, a new watch (that is fully charged) will be available for them to take. Once data are collected, it will be analyzed for sleep/wake cycles and overall activity level. Total activity will be measured as average acceleration over 24 hours. Patterns of acceleration will also be noted relative to treatment times in 2 hour increments.

At baseline and at the beginning of each cycle of TMZ, the patient will complete a sleep questionnaire that will be used in conjunction with the ActTrust watch. This qualitative data (sleep questionnaire) will be used with the quantitative data (collected via the ActTrust watch) to assess the level of disruption in sleep/wake cycles experienced by the patient while on study. This data will be collected up to 1 month after the last TMZ treatment. These sleep questionnaires will be administered during an office visit by the study coordinator.

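### The sleep correlation analysis in 13.2.1 uses an R² cut-off as a significance rule and a contingency-table test for slopes, and leaves response, PFS and OS off its variable list

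*Combined protocol and SAP*

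**What the plan says.** Secondary objective 5 (section 2.2) is: "To correlate the sleep-wake cycles of patients receiving temozolomide for treatment of HGG with treatment outcomes for morning versus evening TMZ treatments". The matching endpoint (section 13.1.2) is: "Correlation between sleep pattern and response to treatment in morning and evening groups".

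The analysis is one paragraph of section 13.2.1. It has three elements.

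- A correlation analysis, with significance declared at R² ≥ 0.8. No alpha, p-value or sidedness is given.
- A "slope analysis (Fisher's Exact Test) of dependent variables (naps/day, nap duration, sleep duration" and four more: percent activity during waking, percent activity during sleep, chronotype and chronotype variability.
- A set of "independent variables (tumor grade, time since TMZ administration, time of day of TMZ administration, time since diagnosis date, tumor size, immune health".

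On the unit of analysis it says: "Each variable will be calculated daily and averaged over the collection period".

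The same section calls analyses of this kind exploratory, has each cohort analysed separately, and states: "The uncertainty of estimates will be assessed by confidence intervals". It also analyses duration of RANO response and PFS by Kaplan-Meier, without reference to sleep. OS is a secondary endpoint, but 13.2 names no method for it.

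**The concern.** There are three separate problems.

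1. R² measures the share of variance explained. A fixed R² cut-off has a false-positive rate and a power that depend on the number of points, and the paragraph does not settle whether a point is a day, a collection period or a patient.
2. Fisher's Exact Test compares counts in a contingency table. Sleep duration, nap duration and chronotype are numeric, naps per day is an averaged count, and no categories are defined. The sentence cannot be carried out as written.
3. The objective is about sleep and treatment outcome, yet the variable list contains no RANO response, PFS or OS.

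Section 2.0 states the purpose: "This exploratory study will collect pilot data for assessment of treatment outcomes in future glioma chronotherapeutic studies". A strong association reported as not significant, or one reported as significant from a handful of points, would mislead the planning of those studies. The link between sleep and outcome would also have no stated method.

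**Working it through.** **Inputs from the documents.** R² ≥ 0.8, seven sleep measures and six other variables (13.2.1); 40 patients (13.0); 1:1 allocation, so about 20 per arm (4.4).

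**Assumptions not in the documents.** Bivariate-normal pairs, one pair per patient for the power figures, and a two-sided 5% test as comparator, unadjusted and at 0.05/42.

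**Step 1: what error rate does R² = 0.8 imply?** It corresponds to |r| = √0.8 = 0.894. The test statistic is t = √(0.8(n−2)/0.2) = 2√(n−2), on n−2 degrees of freedom.

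| n | t | two-sided p at R² = 0.8 |
|---|---|---|
| 4 | 2.83 | 0.106 |
| 5 | 3.46 | 0.041 |
| 10 | 5.66 | 4.8e-4 |
| 20 | 8.49 | 1.0e-7 |
| 40 | 12.33 | 7.5e-15 |

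No single significance level corresponds to the rule.

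**Step 2: what cut-off would a test use?** Critical R² = t²/(t² + n − 2), where t is the two-sided critical value. The lists give 7 × 6 = 42 pairs, so 42 × 0.05 = 2.1 false positives are expected at an unadjusted 5%. A Bonferroni level is 0.05/42 = 0.00119.

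| n | critical R² at 0.05 | critical R² at 0.05/42 |
|---|---|---|
| 10 | 0.399 | 0.750 |
| 20 | 0.197 | 0.451 |
| 40 | 0.097 | 0.244 |

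**Step 3: how often is a true correlation of 0.7 flagged?** (Simulation, 400,000 samples per n.)

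| n | R² ≥ 0.8 | p < 0.05 | p < 0.05/42 |
|---|---|---|---|
| 10 | 7.5% | 68% | 13% |
| 20 | 1.1% | 96% | 62% |
| 40 | 0.03% | >99.9% | 98% |

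**Step 4: the trial's own contrast.** If time of day of TMZ is treated as morning or evening at 1:1, R² = d²/(d² + 4), where d is the mean difference in within-group SDs. Setting R² = 0.8 gives d² = 16. Sleep would have to differ by 4 SDs between arms to meet the rule.

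**Step 5: objective against variable list.** Objective 5 needs treatment outcomes, and endpoint 5 needs response to treatment, by arm. The list offers three related items:

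- tumor size, whose measurement is set out in 11.2 to 11.3.1, although the summary to be correlated is not stated;
- immune health, which is not defined;
- time of day of TMZ.

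RANO response category, PFS and OS are on neither side of the list. The Kaplan-Meier analyses elsewhere in 13.2.1 do not involve sleep.

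**The case against.** The best defence is that this is a small descriptive study. The analysis is declared exploratory, confidence intervals are promised, and the primary feasibility endpoint does not depend on it. All of that stands, and it limits the harm. It does not make Fisher's Exact Test applicable to a slope, and it does not supply the missing outcomes. A Fisher r-to-z comparison may have been intended, but the text does not say so.

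An unadjusted 5% comparator flatters the alternative, because 42 pairs are in play. That is fair, and the 0.05/42 column answers it: the R² rule is still far stricter at n=20 and n=40.

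The four-point case is weakly grounded. It needs a within-patient correlation over about eight months of two-monthly averages, which no section describes, and 7.2 calls about 60 days of recording typical. One average per patient per period is the more natural reading. The four-point figure therefore shows only why the unit must be stated.

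A reader might infer that 13.2.1 ignores RANO and PFS, or that objective 5 has no analysis. The documents do not support either. Duration of response and PFS are analysed by Kaplan-Meier, tumor size is the main measured component of RANO response, and the by-arm element is covered by the time-of-day variable and separate cohort analysis.

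A reader might also infer that the plan would produce a biased sleep–survival estimate from averages over the whole recording. It proposes no such model, so this is a caution for the replacement analysis and not a defect in the plan.

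**Conclusion.** The point holds in this form: the R² rule is mislabelled, the slope test is inapplicable, and the correlation list reaches objective 5 only through tumor size, immune health and time of day. The first two follow from the text and from what the methods do. The third follows from comparing the list with the objective and endpoint.

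The rule's effect depends on the unit of analysis. With one pair per patient, it would miss a true correlation of 0.7 in about 99% of samples at n=20 and nearly all at n=40. Those figures rest on the assumed bivariate normality and the chosen value of 0.7; the p-values in step 1 need only the usual assumptions of the correlation test. Whether the sleep–outcome method would be chosen after the data are seen cannot be established: 13.2.1 mentions an SAP, but nothing in the documents provided fixes that method.

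This is worth correcting before analysis. It does not threaten the trial's primary conclusion.

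**What to change.** Rewrite the correlation paragraph of 13.2.1.

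- Delete the R² ≥ 0.8 rule and Fisher's Exact Test for slopes.
- Report Pearson or Spearman correlations, and regression slopes, with 95% confidence intervals. Use one value per patient per stated window, or a patient random effect if daily values are used.
- Define immune health and state which tumor-size summary is used.
- Add response, PFS and OS as outcomes, by arm and descriptively, for example a Cox hazard ratio per SD of the sleep measure, with its interval, for PFS and OS.
- For PFS or OS, take sleep from a fixed early window (for example the first 28-day cycle) with a landmark at its end. The watch is worn "to measure activity level during the day and at night until two months after the end of treatment", while PFS runs from the start of treatment (11.3.6), so a whole-recording average can include days after progression.
- Report every pair examined as exploratory, noting that the present lists give about 42.

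**Cost.** No added patient burden and some extra analysis work. The calendar (9.0) and form list (10.0) show no response form, so RANO category may have to be abstracted from the chart.

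Intervals will be wide. From tanh(atanh r ± 1.96/√(n−3)), an observed r of 0.5 gives 0.22 to 0.70 at n=40 and 0.07 to 0.77 at n=20. A per-SD hazard ratio is known to within a factor of exp(1.96/√events), which is 1.55 with 20 events and 1.43 with 30 (assumed counts).

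A landmark loses patients with earlier events. Under exponential PFS with an assumed median of 6 or 12 months, 1 − exp(−ln 2 × t/median) gives about 10% or 5% at 4 weeks. Response categories may be sparse, because patients with only nonmeasurable disease cannot be classed as CR or PR (11.1).

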### **5.0 STUDY PLAN**

#### **5.1 Study Procedures**

Temozolomide will be given as per standard of care. Typical dosing is 150 to 200 mg/m^2 on Days 1 through 5 of a 28-day treatment cycle. Patients will be randomized to take their temozolomide doses in the morning (before 10:00) or evening (after 20:00). Compliance with dosing times will be verified by means of a medication diary (Appendix B). Patients who miss taking their dose at the assigned time will be instructed to take the dose as soon as they can (as long as the next scheduled dose is at least 12 hours away) rather than omitting it.

Patients will be given an ActTrust Condor Instrument watch after signing the consent form. Patients will be required to wear the ActTrust Condor Instrument watch 24 hours per day; it should only be removed at specified data collection time points (see protocol calendar 9.0). Actimetry data will be collected at corresponding time points with the return of the patient to clinic every 8 weeks. The ActTrust watch does not require the patient to charge the device, thus the patient will never have to remove the watch and a new, fully charged, watch will be provided to the patient at every collection time point.

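### Section 13.2.1 does not say whether dosing time of day is the assigned arm or the diary time; if it is diary time within each arm, patient-chosen dosing can produce a correlation with chronotype without any drug effect

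*Combined protocol and SAP*

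**What the plan says.** Section 13.2.1 plans correlation analysis, with R² of at least 0.8 as the criterion, between a set of sleep and activity measures and a set of explanatory variables. The dependent measures are "naps/day, nap duration, sleep duration, % activity during waking, % activity during sleep, chronotype, chronotype variability". The explanatory side is "independent variables (tumor grade, time since TMZ administration, time of day of TMZ administration, time since diagnosis date, tumor size, immune health". On the level of calculation it says "Each variable will be calculated daily and averaged over the collection period". It also states: "Each cohort will be analyzed separately, and no multiplicity adjustment across cohorts will be" performed. Cohort is not defined.

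Section 7.2 defines the key sleep measure as "chronotype (average time of daily mid-sleep"), taken from on-study wrist recording. Section 5.1 sets the dosing rule: "Patients will be randomized to take their temozolomide doses in the morning (before 10:00) or evening (after 20:00"). The same section has compliance with dosing times checked by a medication diary and adds "Patients who miss taking their dose at the assigned time will be instructed to take the dose as soon as they can", provided the next scheduled dose is at least 12 hours away. Section 4.4 randomises 1:1, and section 13.0 plans 40 patients.

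**The concern.** Randomisation fixes only the window. Inside it the patient picks the time and has to be awake. Waking is therefore a lower limit for a morning dose, and bedtime an upper limit for an evening dose. The make-up instruction can add to this, because a late riser may take the morning dose on waking after 10:00. Chronotype is itself a clock time, the middle of sleep. Within one arm, sleep timing may thus drive dosing time, while the plan lists sleep as dependent and dosing time as independent.

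Section 2.0 says the study is to supply pilot data for later glioma chronotherapy studies, and section 1.7 names rest-activity rhythm among the means of assessing the timing hypothesis. A sizeable within-arm correlation read as an effect of dosing time on sleep would be a poor basis for the next trial. The comparison that randomisation protects, morning arm against evening arm, is not specified for any sleep measure.

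**Working it through.** **Which comparison each reading gives**

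| Dosing time of day means | Each arm separately | Both arms together |
|---|---|---|
| Diary clock time | Only patient-chosen variation | Mainly the randomised gap, plus some patient choice |
| Assigned slot | Constant, so no correlation can be computed | The randomised contrast |

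Daily calculation and the diary favour clock time. The arms are the only groups the design creates, so separate cohorts most naturally means separate arms. That points to the top-left cell, by inference.

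**Inputs.** From the plan: windows before 10:00 and after 20:00, 40 patients at 1:1 (20 per arm), cut-off R² ≥ 0.8. The plan gives no error rate or effect size for this analysis, so there is no figure to reproduce. Assumed: mid-sleep mean 03:00 with SD 1.0 or 1.5 h; sleep duration mean 8 h, SD 1 h; 10 doses per 8-week period; no effect of dosing on sleep. Morning dose = wake time + 0.75 h + patient habit + daily noise, held to 10:00 at the latest. Evening dose = bedtime − 0.5 h + habit + noise, held to 20:00 at the earliest. Habit SD is 0.25 to 1.0 h and daily noise SD 0.5 h.

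**By hand, ignoring the window limits.** Wake time is mid-sleep plus half of sleep duration, so

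R²(mean dose time, mid-sleep) = V / (V + 1²/4 + h² + 0.5²/10), with V the mid-sleep variance and h the habit SD.

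- SD 1.0 h, h = 0.25: 1/(1 + 0.25 + 0.0625 + 0.025) = 1/1.3375 = 0.75
- SD 1.0 h, h = 1.0: 1/2.275 = 0.44
- SD 1.5 h, h = 0.25: 2.25/2.5875 = 0.87
- SD 1.5 h, h = 1.0: 2.25/3.525 = 0.64

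For sleep duration the numerator is 0.5² = 0.25 over the same denominators. That gives 0.19, 0.11, 0.10 and 0.07, which is much weaker.

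**Simulation with the window limits (4,000 null trials per setting, n = 20 per arm)**

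| Dosing behaviour | Mid-sleep SD | Median R² with chronotype | R² ≥ 0.8 |
|---|---|---|---|
| Habit tied to waking or bedtime | 1.0 h | 0.44–0.76 | 0–32% |
| Same | 1.5 h | 0.63–0.86 | 6–83% |
| Random waking time inside the window, or on waking if after 10:00 | 1.0 h | 0.64 | 8% |
| Same | 1.5 h | 0.79–0.80 | 44–49% |

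In the last two rows, sleep duration reaches p < 0.05 in 24 to 43% of trials, against a nominal 5%.

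**How far the link matters.** A second null model let dose time move fully, half or not at all with wake time or bedtime. It used mid-sleep SD 1.0 h, independent lag SD 0.25 to 1 h and sleep-duration SD 0.5 or 1 h. With a half link, mean within-arm R² is 0.22 to 0.76 and 0.8 is crossed in 0 to 39% of trials. With no link, mean R² is 0.05 and p < 0.05 occurs in about 5%: no artefact. At the other extreme (full link, lag SD 0.25 h, no variation in sleep duration), mean R² is 0.94 and 0.8 is almost always crossed.

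**Arms pooled.** In the habit model the mean dose times are 7:45 and 22:30, a gap of 14.75 h. Between-arm variance is (14.75/2)² = 54.4, against a within-arm variance of 1.3 to 3.5. At SD 1.0 h, h = 0.25, R² is about 1/(54.4 + 1.34) = 0.02. Simulated mean R² is 0.03 to 0.06 and never reaches 0.8. With sleep-linked dosing, p < 0.05 occurs in about 7 to 20% of trials.

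**Assigned arm as the factor.** Mean R² is about 0.03 and p < 0.05 occurs in 4 to 6% of trials in every scenario.

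**The case against.** The documents nowhere say that patients dose on waking or at bedtime, nor that the variable is the time actually recorded. Sections 2.1 and 13.1.1 use administration time for the assigned slot, and cohort may not mean arm. If the arms are pooled, the randomised gap supplies nearly all the variation and the artefact almost disappears. Section 13.2.1 presents results descriptively and calls such analyses exploratory, and its list includes variables such as tumor grade that nobody would read as interventions.

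Much of this stands. The clock-time reading and the dosing-sleep link are inferences, and without the link there is no artefact. But a strict habit is not needed: dosing at a random waking moment inside the window still gives a median R² of 0.64 to 0.80. An exploratory label does not tell a reader which of the four comparisons was made.

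A reader might infer three stronger things. The first is that the plan will report a false dosing-time effect. At mid-sleep SD 1.0 h the habit model's median R² lies below the plan's own 0.8 cut-off, so this is not established. The second is that all seven sleep measures are affected. Chronotype is the main case and sleep duration a weaker one; naps and activity percentages were not examined. The third is that secondary objective 5 is compromised. That objective relates sleep-wake cycles to treatment outcomes, and this analysis lists no treatment outcome.

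**Conclusion.** The point holds as a conditional one. The dosing-time factor and the cohort are undefined. On the likelier reading the analysis uses only non-randomised variation, which may be driven by sleep itself. Under sleep-linked dosing and the assumed sleep variation, the median within-arm R² with chronotype is about 0.45 to 0.86 at n = 20, and 0.8 is crossed in about 0 to 83% of null trials. Weaker or tighter links move these figures down or up. If the variable is the assigned slot, it cannot be correlated with anything within an arm. Only the assigned slot across both arms gives the randomised contrast, and the text does not specify that. The consequence is limited to an exploratory analysis, but the wording should be settled before the data are analysed.

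**What to change.** In section 13.2.1, define the dosing-time factor as the assigned arm, analyse both arms together for this factor, and report for each sleep variable the evening-minus-morning difference with a 95% CI. Report diary clock times within an arm only descriptively, as dosing behaviour or adherence and not as an effect of temozolomide. State what cohort means.

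The cost is SAP wording; no new data are needed. The small downside is that the within-window gradient in dose time is no longer offered as an effect estimate. As a guide to precision, with 20 evaluable patients per arm the CI half-width for chronotype would be 2.024 × SD × √(2/20): 0.64 h at an assumed SD of 1.0 h and 0.96 h at 1.5 h.
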